439 *within 3 weeks after randomization.*

440 **2.4 Randomization of Eligible Subjects**

441 1. Prior to randomization, the study participant's understanding of the trial, compliance with
442 device use, willingness to accept the assigned treatment group, and commitment to the follow-
443 up schedule will be reconfirmed.
444
445 2. Randomization is completed on the DRCR.net website.
446 • Study participants will be assigned randomly (stratified by site and intravitreous treatment*
447 in the non-study eye) with equal probability to one of two treatment groups:
448 ○ Active treatment (670nm wavelength) device
449 ○ Sham (broad spectrum white light) device
450

451 *Randomization will be stratified by site and recent (within 4 months) or planned intravitreous
452 treatment in the non-study eye, including intravitreous anti-VEGF and steroid
453

454 3. For participants who consent, a second randomization will determine whether the participant
455 will receive periodic text message reminders regarding device compliance.
456 • Randomization is completed on the DRCR.net website and will be stratified by assigned
457 treatment group.

458
459 Once a study participant is randomized, that participant will be counted regardless of whether the
460 assigned treatment is received. Thus, the investigator must not proceed to randomize an individual
461 until he/she is convinced that the individual is eligible and will accept whichever treatment group
462 is assigned through randomization.
463

464 **CHAPTER 3: RANDOMIZED TRIAL PROCEDURES**

465 **3.1 Study Device**

466 **3.1.1 Home Procedures**

467 While a device is assigned, the study participant will be required to use the device twice daily
468 (once in the morning and once before bed) for 90 seconds each. Participants will be provided with
469 instructions to take home for proper device use and the required timing of treatments.

470

471 **3.1.2 Primary Outcome Phase**

472 Each participant will receive the type of device for home use based on their treatment group
473 assignment (the participant will remain masked to whether the device is emitting active or sham
474 treatment):

475 ○ Active treatment (670nm wavelength) device twice a day for 90 seconds
476 ○ Sham (broad spectrum white light) device twice a day for 90 seconds

477

478 The primary outcome phase will last until completion of the '4-month' visit, which could be up to

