279 prescribed sessions of the study device use completed during Phase 1) versus magnitude of

280 treatment effect (defined as the change in OCT CST from baseline at the primary outcome visit).

281 The analysis will include all randomized eyes. Eyes that are lost to follow-up or receive an

282 alternative DME treatment will be considered missing for change in OCT CST and compliance,

283 from the time of dropout or initiation of alternative DME treatment. Markov chain Monte Carlo

284 (MCMC) multiple imputation will be used to handle missing data for change in CST and

285 compliance. For eyes receiving alternative DME treatment, after the multiple imputation is

286 performed, the imputed change in CST will be replaced with the last observed CST prior to

287 receiving treatment (i.e. LOCF will be used). The imputation model will be stratified by

288 treatment group and will include the CST measured at baseline and at all monthly interim visits

289 through Phase 1, cumulative compliance (as defined above) through Phase 1, number of days

290 from randomization to the last completed visit (through Phase 1), along with the randomization

291 stratification factor of recent or planned intravitreous treatment in the non-study eye. For eyes

292 that complete the primary outcome visit, the actual visit date will be used for calculating the

293 number of days since randomization, regardless of alternative DME treatment; for eyes that are

294 lost to follow-up, the target visit date will be used. The distribution of the total number of

295 sessions through the primary outcome visit will be described using summary statistics and

296 graphical methods. A scatter plot with a regression line will be constructed to examine for

297 evidence of dose-response, separately for each treatment group.

298 As a dose-response effect is expected only in the active treatment group, and the study is not

299 powered to detect a significant interaction between treatment and compliance, a stratified

300 analysis will be performed using the imputed dataset at the primary outcome visit to evaluate the

301 potential association between compliance and treatment effect separately within each treatment
302 group. The stratified analysis will include adjustment for baseline CST, randomization
303 stratification factor, and number of days from randomization to the primary outcome visit. Model

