330 Adherence in Phase 2 will be evaluated only among eyes participating in Phase 2. The protocol
331 specifies that if alternative treatment is given during Phase 2, participation in the study will be
332 discontinued following next study visit. Missing data will be handled similarly to the Phase 1
333 analysis.

334 In addition, for each phase the effect of text message reminders on compliance will be evaluated
335 using the imputed dataset. Compliance will be defined as the total number of sessions of the
336 study device use during each phase divided by the total number of possible treatment sessions
337 based on visit completion status and alternative DME treatment as noted above; and only
338 participants who have been randomly assigned to receive or not receive text messages will be
339 included in this analysis. This analysis will consist of a comparison of mean compliance between

340 those receiving texts and those not receiving texts using analysis of covariance, and will include
341 treatment, number of days from randomization to the primary outcome visit for Phase 1 (and
342 number of days from the primary outcome to 4 months post outcome visit for Phase 2), and an
343 interaction between treatment group and text message reminders, given it is possible that the
344 participants who are assigned to the control group are less compliant and more likely to ignore
345 text messages. However, it is also recognized that the power for testing the interaction is low in
346 this study due to the limited sample size. If a significant interaction is not present, the analysis
347 will be conducted combining the two treatment groups. If a significant interaction between
348 treatment and text message reminders is present, a stratified analysis will be performed.

349 **5.0 Safety Analysis**

350 All reportable adverse events will be categorized as study eye or systemic. All events will be
351 tabulated by treatment group in a listing of each reported Medical Dictionary for Regulatory
352 Activities (MedDRA) term and summarized over each MedDRA System Organ Class. All
353 randomized participants will be included in safety analyses.

354 Since there are no known risks of the device, there are no pre-specified safety outcomes of
355 interest. However, the frequency of each ocular adverse event occurring at least once per eye and
356 each systemic event occurring at least once per participant will be calculated.

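### The text-reminder effect on compliance is estimated from imputed data whose imputation model omits text assignment, and the Phase 2 model carries terms that cannot be estimated (low severity)

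*SAP*

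**What the plan says.** Text reminders are a second randomised factor. Protocol 2.4 states: "For participants who consent, a second randomization will determine whether the participant" is sent periodic reminders, with that randomisation stratified by device group. The allocation ratio is not given.

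SAP 4.0 treats compliance as missing "from the time of dropout or initiation of alternative DME treatment. Markov chain Monte Carlo" multiple imputation then fills it in. The model is stratified by "treatment group and will include the CST measured at baseline and at all monthly interim visits"; the list goes on "through Phase 1, cumulative compliance (as defined above) through Phase 1, number of days" to the last completed visit, and it closes with the randomisation "stratification factor of recent or planned intravitreous treatment in the non-study eye. For eyes". Text assignment is not in the list, and no other part of the SAP adds it.

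Later in SAP 4.0: "In addition, for each phase the effect of text message reminders on compliance will be evaluated" and, directly after, "using the imputed dataset. Compliance will be defined as the total number of sessions of the" device, divided by the sessions possible given visit completion and alternative treatment. The model is an ANCOVA on text, treatment, number of days and an "interaction between treatment group and text message reminders, given it is possible that the" control group may ignore texts more often. If the interaction is not significant the two groups are combined; if it is, they are analysed separately. All this applies to each phase.

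SAP 2.2 sets the compliance denominator: up to the primary outcome visit for completers, up to device return for non-completers, and up to the start of alternative treatment for anyone treated. SAP 3.0 reports Phase 2 compliance for the initial sham group only, since the active group has stopped using the device.

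**The concern.** An imputation model should contain every factor that the analysis will test. If it does not, values are drawn as though the factor had no effect beyond what the other variables carry, and the estimate made from those draws moves toward no effect. The SAP knows this. In 2.1.4 it runs subgroup interactions on non-imputed completers' data because it regards an imputed analysis as biased when an interaction is present, and Sensitivity Analysis #2 adds a covariate to the imputation model to suit its purpose. The text analysis does neither.

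The plan also gives two accounts of what compliance is for a participant who stops early, and so of how much is imputed. And the model meant for two device groups is carried into a phase in which only one group has a device.

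At stake is a small randomised comparison within the trial: whether reminders raise device use, and whether they do so differently by device group.

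**Working it through.** **Inputs from the documents.** The plan gives no sample size, power or expected missingness for the text comparison. The nearest figure is the 10% loss in Protocol 7.3.2. It reproduces: a two-sample t-test for a difference of 30 microns, SD 50, two-sided 5% and 90% power needs 60 per arm, 120 in total, and 120 / 0.90 = 133.3, rounded up to 134.

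**Assumptions.** True text effect 10 percentage points; SD 25 points; everyone text-randomised 1:1; missingness unrelated to text; the same text effect on earlier and on final compliance. The missing share m and the correlation ρ between earlier and final compliance are varied.

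**Shrinkage.** Let δ be the text effect. Participants with observed compliance contribute a difference of δ. With text left out, imputed values differ between text groups only through earlier compliance, so they contribute about ρδ. Hence

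expected estimate ≈ (1 − m)δ + mρδ = δ[1 − m(1 − ρ)].

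A simulation (134 participants, imputation by device group, 20 imputations, Rubin's rules, 1,500 trials per setting, simulation error about 0.01) gives the second figure in each cell, as estimated effect over true effect:

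| Missing | ρ = 0: formula / simulated | ρ = 0.5 | ρ = 0.8 |
|---|---|---|---|
| 5% | 0.950 / 0.968 | 0.975 / 0.960 | 0.990 / 0.982 |
| 10% | 0.900 / 0.901 | 0.950 / 0.962 | 0.980 / 0.985 |
| 15% | 0.850 / 0.855 | 0.925 / 0.936 | 0.970 / 0.981 |
| 20% | 0.800 / 0.794 | 0.900 / 0.906 | 0.960 / 0.965 |
| 30% | 0.700 / 0.694 | 0.850 / 0.868 | 0.940 / 0.957 |

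At 10% missing, 10 points becomes 10 × 0.90 = 9.0 to 10 × 0.98 = 9.8. Simulated power is 0.48 to 0.59, against 0.60 to 0.63 with text in the imputation model. With text included, the ratio is 0.98 to 1.02 in every setting.

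**Interaction.** If both device groups have the same m and ρ, each text effect is multiplied by the same factor f = 1 − m(1 − ρ), so the interaction fδ(active) − fδ(sham) shrinks by f as well.

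**How much is imputed.** Take a participant who stops early. Under the SAP 4.0 missingness rule, compliance from that point is missing and is imputed. Under the SAP 2.2 denominator, to which the text paragraph appears to refer back, the ratio ends at device return or at alternative treatment and can mostly be computed from device data. On that reading m is near zero and so is the shrinkage, but the instruction to use the imputed dataset then has little to act on. The two cannot both be followed.

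**Phase 2.** The stated model has five columns: intercept, treatment, text, treatment × text and days. Compliance exists only in the initial sham group, so treatment is constant. Coded 0, treatment and treatment × text are columns of zeros; coded 1, they duplicate the intercept and text. Either way the rank is 3. With treatment and its interaction dropped, intercept, text and days have rank 3 of 3. In Phase 1 the matrix has rank 5 of 5.

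**The case against.** Three arguments on the other side carry weight.

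First, a reader might infer that the loss of effect equals the missing fraction. The documents do not support that as the expected size. Cumulative compliance is in the imputation model, and what a participant did before stopping already reflects any text effect. Only when earlier compliance says nothing about later compliance (ρ = 0) does the shrinkage reach the missing share. That is about the upper bound.

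Second, if the SAP 2.2 denominator governs, little is imputed and the bias nearly vanishes. This is fair, and it is why the bias is stated conditionally. It does not clear the plan, because the plan also calls for imputed data under a missingness rule that contradicts that denominator.

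Third, a reader might infer that the Phase 2 analysis cannot be fitted at all. It can: SAP 3.0 and 4.0 already confine Phase 2 compliance to the initial sham group, and software that drops redundant terms returns a text effect adjusted for days. What stands is that the interaction test and the combine-or-stratify rule have no meaning there. Protocol 7.12 has the same redundancy, since it adjusts for treatment in each phase.

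On importance, the compliance inputs that SAP 6.0 names for the pivotal trial are examples: the proportion of enrolled participants who are randomised and the proportion who comply. The text effect is not named, so nothing shows that the pivotal design depends on it. The SAP also concedes low power for the interaction.

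**Conclusion.** The point holds, at low severity. To the extent that compliance is imputed, omitting text assignment biases the text effect and its interaction with treatment toward zero: by about 2% to 10% at the planned 10% loss and 4% to 21% at an assumed 20%. The ranges rest on assumed correlations of 0 to 0.8, an assumed effect of 10 points and SD of 25 points, and equal missingness across groups. Eyes given alternative treatment would add to the missing share, and the documents do not project their number. The conflict between the missingness rule and the denominator, and the inestimable Phase 2 terms, rest on no numerical assumption. The primary CST comparison does not use this imputed compliance, so its conclusion is unaffected.

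**What to change.** 1. State one compliance definition for the text analysis and reconcile SAP 2.2 with SAP 4.0.
2. Then take one route. Either use observed compliance with the SAP 2.2 denominator, without imputation; or, if imputing, add text assignment to the imputation model within the existing device-group stratification. Because the imputation covers all randomised eyes, code text as assigned, not assigned, or not text-randomised. Stratifying by device group already allows the text effect to differ between groups, so no separate interaction term is needed. Do not split the imputation further by text group: 134 / 4 gives at most about 33 participants per cell, for a model with five CST time points plus compliance, days and the stratum.
3. For Phase 2, restrict the model to the initial sham group with text and days, and say that the interaction test and the combine-or-stratify rule apply to Phase 1 only.

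The cost is at most one variable already recorded and a few sentences. No new data are needed.

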 513 (because of unforeseen circumstances) are unable or unwilling to return for all follow-up visits
 514 will be permitted to return for key visits only as an alternative to withdrawal from the study.
 515 Participants who are not using a device during the post-outcome phase but have not received
 516 alternative treatment will be given the option to continue study visits or end study participation
 517 early.

518

519 Additional phone contacts may be performed as needed.

520 **3.2.1 Text Message Reminders**

521 For participants randomly assigned to text message reminders, periodic messages will be sent by
 522 the Coordinating Center with a reminder to comply with the study device schedule.

523 **3.3 Procedures at Study Visits**

524 The following procedures will be performed in both groups at each visit, unless otherwise
 525 specified:

- 526 1. E-ETDRS visual acuity testing (best corrected) in each eye.
 - 527 • A protocol refraction in the study eye is required at each visit. Refraction in the non-study
 528 eye is only required at the 4 and 8 month visits. When a refraction is not performed, the
 529 most recently performed refraction is used for the testing.
- 530 2. Spectral-Domain OCT using Zeiss Cirrus or Heidelberg Spectralis in both eyes
 - 531 • The same machine type (Cirrus or Spectralis) used at baseline should be used during
 532 follow-up.
- 533 3. Ocular exam in the study eye, including slit lamp examination with lens assessment,
 534 measurement of intraocular pressure, and dilated ophthalmoscopy.
 - 535 • Required at Primary Outcome and 4-Month Post Outcome visits only. Otherwise,
 536 ocular exam is at investigator discretion. In general, an ocular exam should be
 537 completed if the OCT and/or visual acuity have worsened since baseline (e.g. more
 538 than 10% increase in CSF thickness or 5 letter loss in VA).

539 4. OCT angiography on the study eye if obtained at baseline (4 month/primary outcome visit
540 only)

- 541 • Only obtained by a subset of sites with OCT angiography capabilities.
- 542 • *See procedure manual for more details on acquisition, including which fields to collect*
543 *on a given OCT angiography system.*

544 5. Compliance assessment

- 545 • The site personnel will download the compliance data and re-emphasize the importance
546 of compliance with device use

547 All of the testing procedures do not need to be performed on the same day, provided that they are

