1008 performed to evaluate the potential association between compliance and treatment effect within
1009 each treatment group. Model assumptions will be checked, and transformation or categorization
1010 of compliance will be used if there is evidence of non-linearity in the dose response. It is
1011 recognized that the study is not powered to detect a definitive dose-response association existing
1012 only in the active treatment group and that lack of significance is not necessarily an indication that
1013 the association does not exist. It is also recognized that compliance may be affected by both
1014 measured and unmeasured post-randomization factors, including efficacy of masking and
1015 perceived effects of the treatment; hence, the observed dose-response associations may be biased.
1016

1017 If compliance lessens over time during the primary outcome phase, an exploratory analysis will
1018 investigate whether there appears to be any association of compliance versus magnitude of
1019 treatment effect over those months.
1020

1021 For Phase 2, adherence will be evaluated in a similar fashion for those using the device to assess
1022 whether compliance affects the post-switch effect within group, specifically:
1023

- For the initial treated group, whether there is an association between compliance during
1024 phase 1 and duration of treatment effect in phase 2.
- For the initial sham group, whether there is an association between compliance during
1026 phase 2 and treatment effect in phase 2.
1027

1028 In addition, for each phase the effect of text message reminders will be evaluated by assessing
1029 compliance within each treatment group. Compliance will be defined as the total number of
1030 sessions of the study device use during each phase divided by the total number of possible
1031 treatment sessions. This analysis will consist of a comparison between those receiving texts and
1032 those not received texts of mean compliance using analysis of covariance, with adjustment for
1033 treatment. Only participants who have been randomly assigned to receive or not receive text
1034 messages will be included in this analysis.
1035

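### The SAP adjusts the randomized text-reminder comparison for visit timing, which is set after text assignment; the main analysis should omit that term.

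*SAP*

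**What the plan says.** Protocol 2.4 sets up the reminder assignment: "For participants who consent, a second randomization will determine whether the participant" gets periodic messages, with stratification by treatment group. Protocol 3.2.1 gives the content: messages come from "the Coordinating Center with a reminder to comply with the study device schedule". Visit attendance is not mentioned.

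Protocol 7.12 plans to compare those assigned texts with "those not received texts of mean compliance using analysis of covariance, with adjustment for" treatment. Nothing else is in that model.

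SAP 4.0 keeps the ANCOVA but lists its terms as "treatment, number of days from randomization to the primary outcome visit for Phase 1 (and", continuing, "number of days from the primary outcome to 4 months post outcome visit for Phase 2), and an" interaction of treatment with text group. It explains the interaction (sham participants might ignore messages) but gives no reason for the days term. The outcome is sessions used divided by sessions possible, and the imputed dataset is used.

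Earlier in SAP 4.0, in the dose-response description, the days value is defined. For eyes "that complete the primary outcome visit, the actual visit date will be used for calculating the" day count; for eyes "lost to follow-up, the target visit date will be used". SAP Table 3 lets the primary visit fall from day 84 to day 224. The imputation model listed there is stratified by treatment group. It includes CST, cumulative compliance, days to the last completed visit and the non-study-eye stratification factor, but not text assignment.

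**The concern.** A randomized comparison needs only baseline terms to be valid. Days to the visit is not a baseline term: it is realized weeks to months after text assignment and depends partly on participant behaviour. If reminders make people more engaged, they may also change when, or whether, people attend. Holding days fixed then removes the part of the text effect that runs through timing. Where an unmeasured trait such as motivation drives both attendance and device use, it also introduces an association between text group and that trait.

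The days value is partly assigned as well. A participant who would have been lost is given the target date (16 weeks, day 112), whereas one retained by reminders carries an actual date of up to day 224. Texts could therefore raise or lower the covariate, and the direction of any distortion cannot be known in advance.

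At stake is the only randomized comparison in this trial of a way to raise compliance. Protocol 1.1.5 describes compliance as a significant problem in the earlier light-mask trial.

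**Working it through.** **The plan's own figures.** The documents give no sample size, effect or SD for the text comparison. Their only sample-size figure is for CST: a two-sample t calculation with difference 30, SD 50, two-sided 5% and 90% power gives 59.35, so 60 per arm and 120 in total, and 120/0.90 = 133.3, so 134. It reproduces and is not at issue here.

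**Formula.** Let a be the effect of texts on days, and b the slope of compliance on days given text and treatment. By the usual least-squares identity,

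estimate without days - estimate with days = a × b.

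If a = 0 the two agree on average, whatever b is. If a and b have the same sign a positive text effect is attenuated; if their signs differ it is inflated.

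**Illustration 1 (every input assumed; none is in the documents).** Compliance SD 20 points, days SD 25, correlation -0.30, true total text effect 5 points, 120 participants split evenly.

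- b = -0.30 × 20/25 = -0.24 points per day.
- Visits 3 days earlier: 5 - (3 × 0.24) = 4.28.
- Visits 7 days earlier: 5 - (7 × 0.24) = 3.32.
- Visits 14 days earlier: 5 - (14 × 0.24) = 1.64.
- Visits 7 days later: 5 + (7 × 0.24) = 6.68.
- Visits not moved: 5.

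**Price of dropping the term, same inputs.**

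- SE without days = 20 × sqrt(1/60 + 1/60) = 3.65.
- SE with days ≈ 3.65 × sqrt(1 - 0.30²) = 3.48.
- Ratio = 3.65/3.48 = 1.05, so about 5% wider.

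**Illustration 2 (assumed total effect 10 points; 1,000,000 simulated participants, interaction omitted).** The model without days returned about 10 throughout.

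| Effect of texts on visit date | Estimate with days in the model |
|---|---|
| None, b from -0.1 to -0.3 | about 10.0 |
| 7 days earlier, b from -0.1 to -0.3 | 9.3 to 7.9 |
| 14 days earlier, b from -0.1 to -0.3 | 8.6 to 5.9 |
| 28 days earlier, b from -0.1 to -0.3 | 7.2 to 1.6 |
| 14 days earlier, b = +0.1 | 11.4 |
| 14 days earlier, shared cause only | 7.9 |
| 7 days later, shared cause only | 11.0 |
| None, shared cause only | 10.0 |

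The shared-cause rows have no direct effect of days on compliance. Even there, the estimate shifts only when texts move the visit.

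**Imputation.** Because text assignment is not in the listed imputation model, imputed compliance reflects text group only indirectly, through earlier compliance and visit timing. As a rough guide, if 10% of values were imputed (the loss planned in Protocol 7.3.2) and carried no text information at all, a 5-point effect would shrink to 0.90 × 5 = 4.5. Removing days from the ANCOVA does not cure this.

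**The case against.** The strongest reply is that nothing in the documents says texts affect visit dates. The messages concern device use. Scheduling is supported separately by Coordinating Center phone contacts (Protocol 6.6.1), with no distinction by text group. The SAP revision history records that the primary-visit window was lengthened by 8 weeks as a COVID-19 response, so much of the spread in days may have nothing to do with texts. In that case the covariate is harmless and slightly helpful. This stands: the bias is conditional.

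The illustrations can also be called generous. An effect of 5 points is 5/20 = 0.25 SD of compliance, whereas shifts of 7 and 14 days are 0.28 and 0.56 SD of days, so a device-use message is assumed to move visits more than device use. The 3-day case (0.12 SD) costs about 0.7 points against an SE near 3.5. With the same inputs, 5/3.65 = 1.37, so two-sided power is only about 28%. Low power would more often hide a useful reminder than this covariate would.

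Four stronger readings are tempting, and the documents do not support them:

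- **That the adjustment necessarily breaks the randomized comparison.** It does so only if texts move visit timing.
- **That it will make reminders look ineffective.** The shift can go either way.
- **That duration is irrelevant because compliance is already a proportion.** Dividing by possible sessions does not remove waning. Protocol 7.12 and SAP 4.0 both allow for compliance falling over time, so over a window of 84 to 224 days the term could well be prognostic.
- **That the protocol and SAP contradict each other, or that the pivotal trial rests on this result.** Protocol 7.1 describes its chapter as a synopsis. The pivotal-design passages (Protocol 7.19, SAP 6.0) name compliance in general, not the text effect.

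What remains is that the SAP's only text model carries an unexplained post-assignment term, and a reader of the result could not tell which case applied.

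**Conclusion.** The point holds in conditional form. Both days terms are set after text assignment, and the model in Protocol 7.12 does not contain them. If texts change visit timing, the SAP estimate is not the total text effect and errs by the product a × b, in either direction; if they do not, the error is zero. The sizes shown (5 points becoming 4.3, 3.3, 1.6 or 6.7) rest wholly on assumed inputs and indicate scale only. The comparison is exploratory, is not among the listed primary or secondary outcomes, and has no bearing on the primary CST conclusion. This is a cheap improvement, not a serious flaw.

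**What to change.** In SAP 4.0:

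1. Make the ANCOVA with text group, treatment and their interaction, without days, the main text-reminder analysis in both phases. In Phase 2 only participants originally assigned to sham use a device, so there the model reduces to text group.
2. Keep the days-adjusted model as a labelled sensitivity analysis, giving possible waning over a wide visit window as its reason.
3. Tabulate visit timing by text group, with participants assigned the target date shown separately. This lets a reader judge whether texts moved the visit.
4. Add text assignment to the imputation model used for this comparison. That model is already stratified by treatment, so a text term within each stratum also accommodates the interaction. Days to the last completed visit can stay in it.

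The within-arm dose-response models can keep their days term.

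The cost is SAP wording and one small table. Precision falls by about 5% if days and compliance correlate at about 0.30 (an assumption), and by less if the correlation is weaker. Phase 2 remains the weaker comparison even so, because who continues with a device is itself decided after text assignment.
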